- In the ANRS 163 ETRAL trial a sample bank will be constituted in order to monitor raltegravir and etravirine plasma concentrations. At specific points these concentrations will be analysed in correlation with trial end-points.

5.6 *Trial hypothesis*

Given the potency of raltegravir and etravirine, and although our limited clinical experience, we bring the hypothesis that a dual RAL/ETR regimen will be able to maintain the viral suppression if the two drugs are fully sensitive namely in patients naïve to both raltegravir and etravirine without any mutation that might impair drug's efficacy.

The second hypothesis is that, in a patient population with long-term ART, of at least 45 years of age, the switch to dual raltegravir/etravirine therapy should limit the long-term toxicity induced by NRTI and PI drugs, in particular cardiovascular, bone and renal diseases, without derogating from the key principle of sustained virological control.

ANRS 163 ETRAL trial should assess:

- The virological safety of raltegravir/etravirine association.
- The impact of the discontinuation of NRTIs, PIs on the distribution of adipose tissue, bone mineral density, metabolic parameters and seminal HIV-RNA viral load.

6 **OBJECTIVES**

6.1 *Principal objective*

To evaluate over 48 weeks of treatment the capacity to maintain virological success defined as the absence of 2 consecutive plasma viral loads (VL) > 50 copies/mL within 2 to 4 weeks of a dual raltegravir/etravirine regimen in HIV-1 infected patients, of at least 45 years of age, with suppressed plasma viremia switching from a boosted PI-containing regimen.

6.2 *Secondary Objectives*

6.2.1 *Biological efficacy*

- To assess the proportion of patients in therapeutic success up to week 48 and week 96
- To assess the proportion of patients with virological success (plasma HIV-RNA \leq 50 copies/mL) up to week 96
- To assess the proportion of patients with an interruption of therapeutic strategy
- To assess the proportion of patients with low grade virological failure (HIV-RNA plasma VL between 51 and 200 copies/mL) and the proportion of patients with high grade of virological failure defined as HIV-RNA >200 copies/mL at time of virological failure
- Time limit to virological failure
- HIV genotypic resistance profile, in plasma, in case of virological failure
- To determine the factors associated with virological rebound (plasma HIV-RNA > 50 copies/mL)

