8.2 Non-inclusion criteria

- Previous exposure to raltegravir or etravirine
- Presence of any documented integrase inhibitor mutation on DNA genotype at W-6/W-4 and/or on RNA in the medical history of the patient.
- Positive hepatitis B HBsAg or Positive HBc Ac and negative HBs Ac
- HIV-2 infection
- Active viral hepatitis C requiring a specific treatment during the 24 months of the trial
- Patient with a history of non-compliance or irregular follow-up
- Initiation of a concomitant anti-hypercholesterolemia (e.g. statins) or anti-diabetic treatment within the last 3 months prior the screening visit (W-6/W-4)
- Patient using: clopidogrel (Plavix®), prasugrel (Effient®), Ticagrelor (Brilinta®), Ticlopidine (Ticlid®), Flurbiprofen (Antadys® - Cebutid®), Rifampin (Rifampicin® - Rifadin® - RofactMC - Rifater®), Rifapentine (Priftin®), St John's wort, Carbamazepine (Tegretol®), Phenobarbital, Phenytoin (Dilantin®), Avanafil (Stendra™), Triazolam (Halcion®).
- Concomitant treatment using interferon, interleukins or any other immune-therapy or chemotherapy
- Concomitant prophylactic or curative treatment for an opportunistic infection
- All conditions (use of alcohol, drugs, etc.) judged by the investigator to possibly interfere with trial protocol compliance, adherence and/or trial treatment tolerance
- Subjects under "sauvegarde de justice" (judicial protection due to temporarily and slightly diminished mental or physical faculties), or under legal guardianship

- Subjects participating in another clinical trial evaluating different therapies and including an exclusion period that is still in force during the screening phase
- Pregnant women or breastfeeding women

9 **STUDY ENDPOINTS**

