9.2 Secondary Endpoints

Biological efficacy

- Percentage of patients remaining in therapeutic success up to week 48 and week 96 defined as the absence of virological failure and the absence of treatment interruption due to adverse event judged by DSMB as related to the trial treatment or procedure
- Percentage of patients in virological success (plasma HIV-RNA \leq 50 copies/mL) up to week 96
- Percentage of patients with trial treatment interruption
- Percentage of patients with plasma HIV-RNA VL between 51 and 200 copies/mL and percentage of patients with plasma HIVRNA VL > 200 copies/mL at time of virological failure
- Median time of virological failure (time limit between the date of the study treatment initiation and the date of virological failure)
- Percentage of patients with RAL and/or ETR resistance mutations in case of virological failure and percentage of patients with resistant viruses to all study drug's class in case of virological failure
- Factors associated with the occurrence of plasma HIV-RNA VL > 50 copies/mL (genotype history, pre-cART VL, plasma drug concentration (etravirine, raltegravir) at the virological rebound, viral reservoir measured by HIV-DNA at D0 and adherence assessed with a self-questionnaire)
- Evolution of total cell-associated HIV-DNA from D0 to W48 and W96
- Evolution of CD4+, CD8+ T cells counts and CD4/CD8 ratio at each time point from D0

Tolerability and Metabolic Impact

- Percentage of patients with at least one serious adverse event as judged by DSMB as related to the trial treatment or to the trial strategy
- Percentage of patients with grade 3 or grade 4 clinical and biological adverse events
- Evolution of metabolic parameters (fasting triglycerides, total cholesterol, HDL-cholesterol, LDL-cholesterol and fasting glycemia)
- Evolution of the calibrated Framingham risk score and of the SCORE risk equation including HDL cholesterol (from the European Cardiovascular Society) from D0 to W48 and W96
- Evolution of renal function measured using proteinuria and the CKD-EPI (Chronic Kidney Disease Epidemiology Collaboration Calculator) formula to estimate the Glomerular Filtration Rate (GFR) from D0 to W96
- Evolution of limb lean, limb fat, visceral adipose tissue (VAT) and subcutaneous adipose tissue (SAT), measured by DXA scan (Dual-energy X-Ray Absorptiometry), from D0 to W48 and W96 (DXA scan sub-study, 80 patients)

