11.11.3 Management of lipid metabolism impairment

In case of mild increase of the lipid parameters, a dietary regime will be proposed. Concomitant lipid-lowering treatments with fibrates or statins are needed. They will have to be prescribed according the guidelines, taking into account the potential interactions with cytochrome P450 based enzymes.

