11.11.4 Management of glycaemia impairment

In case of onset of hyperglycaemia or diabetes, an appropriate treatment should be proposed with a dietary regime, physical exercise and anti-diabetic drugs if needed.

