16.2.2 Statistical methods

The primary endpoint is the virological success up to week 48 defined by the absence of 2 consecutive HIV-RNA plasma VL > 50 copies/mL within 2 to 4 weeks.

The therapeutic success is defined by the absence of virological failure and the absence of treatment interruption due to adverse event judged by DSMB as related to the trial treatment or procedure up to week 96.

In particular:

- Patients with 2 or more consecutive missing HIV-1 RNA plasma viral load values or lost to follow up will be considered as patients with treatment failure (failing patients).
- Patients who discontinue the treatment due to adverse event judged by DSMB as related to the trial treatment or procedure will be considered as failing patients.
- Patients who discontinued the treatment due to adverse event judged by DSMB as NOT related to the trial treatment or procedure will not be considered as failing patients.
- Patients who gave up will not be considered as failing patients.
- Patients who discontinued the trial treatment for any reason other than a virological failure or adverse event judged by DSMB as related to the trial treatment will not be considered as failing patients.
- Patients with a missing HIV-1 RNA value between 2 documented HIV-1 RNA plasma viral loads \leq 50 copies/mL will not be considered as failing patients.

Analysis of the primary endpoint will be performed on both ITT and per protocol populations. The 95% two-sided confidence interval of the percentage of patients in therapeutic success will be calculated and raltegravir/etravirine will be considered as an acceptable strategy if the lower bound is greater than 90%.

The changes in continuous endpoints will be compared in the ITT population (LOCF or other imputation method to be defined in the statistical analysis plan) using a two-sided non-parametric paired Wilcoxon test with a 5 % type I error. We will use percentage and 95 % two-sided confidence interval to describe the qualitative endpoints, their change over time will be tested a McNemar test with a 5 % type I error.

The adverse events leading to a trial treatment discontinuation and the number of patients who discontinued the trial treatment, as well as the number and nature of grade 3 and 4 adverse events will be described.

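### The planned lipid and glucose tests describe the switch plus any drugs added after D0; a supplementary analysis and a count of drug starts are needed before the change is attributed to stopping NRTIs and PIs

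*Combined protocol and SAP*

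**What the plan says.** The endpoint in 9.2 is the "Evolution of metabolic parameters (fasting triglycerides, total cholesterol, HDL-cholesterol, LDL-cholesterol and fasting glycemia". Section 16.2.2 gives the analysis: "The changes in continuous endpoints will be compared in the ITT population", "using a two-sided non-parametric paired Wilcoxon test with a 5 % type I error". Its only data-handling clause is "LOCF or other imputation method to be defined in the statistical analysis plan", which concerns missing values. Section 16.2.3 promises a detailed analysis plan before any analysis; that plan is not among the documents.

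Section 5.6 says the trial should assess "The impact of the discontinuation of NRTIs, PIs on the distribution of adipose tissue, bone mineral density, metabolic parameters and seminal HIV-RNA viral load".

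Drug changes after D0 are foreseen:
- Section 11.11.3: "Concomitant lipid-lowering treatments with fibrates or statins are needed", prescribed according to guidelines.
- Section 11.11.4: "an appropriate treatment should be proposed with a dietary regime, physical exercise and anti-diabetic drugs if needed".
- Section 10.3.1 foresees adjusting several statins, with the lipid response as the guide for atorvastatin, lovastatin and simvastatin.

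The only limit on new starts is the non-inclusion criterion in 8.2: "Initiation of a concomitant anti-hypercholesterolemia (e.g. statins) or anti-diabetic treatment within the last 3 months prior the screening visit (W-6/W-4"). It steadies the baseline and does not reach past D0.

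**The concern.** With one arm, a test of change from D0 asks whether anything moved the lipid or glucose value, whatever the cause. A statin or anti-diabetic drug started in follow-up is one such cause. It is given because the measured value is poor, so some of the worst outcomes are turned into improvements. Values after such a start are observed, not missing, so the imputation clause in 16.2.2 would leave them as they are.

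Two errors are possible if the result is read as the effect of stopping NRTIs and PIs: a decrease may be credited to the switch although a drug produced it, or a worsening may be hidden. Limiting long-term toxicity, cardiovascular in particular, is the second hypothesis in 5.6, and total and HDL cholesterol also feed the risk scores in 12.3.2.

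**Working it through.** The documents give no effect size, SD or power for these endpoints, so there is no planned figure to reproduce. The check applies the planned test to assumed data.

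**Inputs.** From the documents: n = 160, paired Wilcoxon test, two-sided 5 %, one arm. Assumed: changes are normal with SD 1; a fraction f of patients starts a drug after D0; the drug lowers their value by 1.25 SD.

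**Hand approximation at f = 10 %, no switch effect** (mean-based, as a guide to the Wilcoxon result)
- Mean shift = 0.10 × 1.25 = 0.125 SD.
- Variance with random starters = 1 + 0.10 × 0.90 × 1.25² = 1.141, so SD = 1.068.
- Standard error = 1.068/√160 = 0.0844, and 0.125/0.0844 = 1.48.
- Chance of a significant decrease ≈ Φ(1.48 − 1.96) = Φ(−0.48) ≈ 0.32, against 0.025 with no starters.

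**Simulation of the Wilcoxon test, 1.25 SD, 4,000 runs per cell.** Starters are drawn at random, are partly selected (ranked on their change plus noise of equal variance), or are exactly the patients who worsened most.

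| Starters of 160 | False decrease: random / partly selected / worst | Power for +0.25 SD: random / partly selected / worst |
|---|---|---|
| 0 | 2.5 / 2.5 / 2.7 % | 86 / 87 / 87 % |
| 2 % (3) | 3.7 / 4.4 / 3.4 % | 80 / 82 / 85 % |
| 5 % (8) | 9.1 / 11.9 / 8.3 % | 64 / 70 / 80 % |
| 10 % (16) | 25.6 / 35.6 / 26.3 % | 34 / 45 / 63 % |

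The ranges used in the conclusion (3–4 %, 8–13 % and 22–34 % false decreases; 36–64 % power) come from separate runs under varying selection; this table agrees with them to within two points.

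**Sensitivity to the drug effect, random starters.** With shifts of 1.0, 1.5 and 2.0 SD, false decreases are 7.2, 11.6 and 13.4 % at 5 % starters, and 18.7, 30.9 and 41.3 % at 10 %. Power for the worsening at 10 % starters is 45, 23 and 12 %.

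**Does setting aside post-start values help?** Changes at W12, W24 and W48 were simulated with correlation 0.5 (assumed). Ten per cent of patients started after W12 or W24 because of the value measured there. A likelihood-type estimate of the W48 change used the earlier visits (1,000 runs, bootstrap standard errors). False decreases fell from 36 % with the Wilcoxon test to about 4 %. Power for the 0.25 SD worsening rose from 41 % to 87 %. The mean estimates were −0.01 and 0.26 SD, against true values of 0 and 0.25.

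**Would ranking starters as worst be a safe alternative?** Only if they truly are the worst. With random starters and no switch effect, it shows a false worsening in about 17 % of trials at 5 % starters and 54 % at 10 %. When starters are the patients who worsened most, the rate is about 2–4 %.

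**The case against.** The strongest reply is that the objectives and endpoints speak of the modification and evolution of metabolic parameters, and an ITT comparison of all values answers that as a treatment-policy summary: what happens to lipids and glucose when patients switch and receive usual care. This stands. A reader might infer that the planned test is invalid; the documents do not support that. The gap is between the test and the causal wording in 5.6.

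Other points also stand in whole or part:
- **The later plan.** A reader might infer that no rule was ever set. The detailed plan is not available, so this can be said only of the protocol, which hands that plan only the imputation method for these endpoints.
- **Unknown rates.** Neither starter frequency nor drug effect is documented. At 2 % starters the distortion is small.
- **Who starts.** Random selection overstates the loss of power if the worst patients start: about 64 % power remains at 10 % starters, not about 35 %. The false-decrease figures hold up under either selection.
- **Statin exposure.** Section 10.3.1 reports atorvastatin AUC down 32–43 % with etravirine, and section 5.3 says boosted PIs raise simvastatin and lovastatin concentrations. The switch can itself lower statin exposure, so a later dose change may partly restore it. Dose changes should not be treated as new starts.
- **Risk scores.** Section 12.3.2 counts any anti-diabetic treatment as diabetes, so starting such a drug cannot improve that input. Only the cholesterol inputs are open to the problem.

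**Conclusion.** The point holds as a cheap improvement to secondary analyses. The planned test describes the switch plus any drugs added after D0, and by itself it cannot support a statement about the impact of stopping NRTIs and PIs.

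Under an assumed 1.25 SD drug effect and no switch effect, a false significant decrease occurs in about 3–4 % of trials at 2 % starters, 8–13 % at 5 % and 22–34 % at 10 %, against a nominal 2.5 %. Power to show a 0.25 SD worsening falls from about 86 % to about 36–64 % at 10 % starters. These figures rest on normal changes, n = 160, and a starter rate and drug effect that the documents do not give.

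A reader might go further and infer that the lipid improvement mentioned in Appendix A8 came from added drugs. The documents report no number of starters, so they neither support nor exclude this.

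**What to change.** In 16.2.2 or the detailed analysis plan:

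1. Keep the ITT Wilcoxon test and label it as the treatment-policy description.
2. Report how many patients start, or change the dose of, a lipid-lowering or anti-diabetic drug after D0.
3. Add a supplementary analysis that sets aside lipid values after the first new lipid-lowering drug, and glucose values after the first new anti-diabetic drug. Estimate the W48 and W96 changes with a mixed model on the D0, W12, W24, W48 and W96 values.
4. Handle dose changes of existing statins in a separate sensitivity analysis, because the switch itself can alter statin exposure.
5. Use a worst-rank analysis only as a labelled bound, with the direction stated for each parameter (reversed for HDL).
6. For the risk scores, apply the rule to the cholesterol inputs and keep the definition of diabetes in 12.3.2.

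The cost is analysis-plan wording and a few extra analyses. Section 18.4 already has changes in concomitant drugs and dosages recorded, and the visits are in the schedule in 11.1. Patient management is unchanged. The price is slightly wider intervals and reliance on missing-at-random. Diet, time trend and regression to the mean remain uncontrolled in a single arm, so even the supplementary estimate is not a clean causal effect.

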7 EXPERIMENTAL DESIGN

7.1 Main study

ANRS 163 ETRAL is a multicentre non-comparative phase II trial evaluating, in fully suppressed HIV-1-infected patients, of at least 45 years of age, with a suppressed viremia, the capacity of a dual raltegravir/etravirine antiretroviral regimen to maintain the virological success defined as two consecutive HIV-RNA plasma viral loads > 50 copies/mL within 2 to 4 weeks. Eligible patients must be under a stable PI-containing ARV regimen for at least 6 months and they must be fully suppressed within the 24 months prior the screening visit (W-6/W-4), as confirmed by 4 documented viral loads (e.g. 2 measurements per year during the past 24 months and not more than 1 HIV-RNA plasma viral load between 51 and 200 copies/mL).

All PI-containing baseline ARV regimens are eligible except those containing raltegravir and/or etravirine.

At Day 0, patients eligible according all criteria detailed in paragraph 8 will be switched to the dual raltegravir (400 mg BID) plus etravirine (200 mg BID) regimen.

Any SAE considered by the investigator and/or the sponsor as potentially related to the trial treatments will be reviewed and evaluated by DSMB.

For all patients, during the 96 first weeks of the trial, a summary of the virological data including HIV-RNA viral loads and virus strains genotypes will be regularly submitted to the DSMB for review.

The immunologic analysis of the evolution of the inflammation markers will be performed on frozen plasma aliquots from whole blood samples collected at specific time points: D0, W48, and W96. The markers of interest are: IL-6hs, sCD14, sCD163, D-Dimers, IP-10, IgG, CRPus and insulin.

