7.2 Sub-studies

7.2.1 DXA-scan

After signing a sub-study-specific informed consent form, 80 patients will be included in the DXA-scan sub-study assessing the evolution of bone mineral density (BMD) and of body fat distribution, and evaluating the potential impact of the dual raltegravir/etravirine regimen on these two parameters.

DXA-scans will be performed locally in all participating French sites at D0, W48 and W96 with a time limit up to 7 days before the date of D0 visit and with a time limit up to 10 days before and after the visit date of W48 and W96. The acquired images will be electronically transferred to a central review facility for final evaluation.

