11.5.2 Last visit of follow-up

The last visit of follow-up for each patient will be the week 96 visit if the patient completes the trial or the EOT visit in case of giving up or premature stop. Patients who stop the trial treatment will continue to be followed according to the trial calendar until the week 96.

- **W96 Visit:** the investigator will realize a clinical examination (blood pressure, heart rate, body temperature, targeted physical examination, weight), anthropometric measurements (specific circumferences: abdomen (perimeter at the umbilicus) and hips (bi-trochanterian perimeter), check the presence of intercurrent pathologies and the treatments intake. Cardiovascular risk factors (arterial hypertension, tobacco, alcohol abuse, physical activity, diabetes) and the measurement of the systolic blood pressure (refer to appendix 7) will be recorded. Urinary pregnancy test for women of childbearing potential will be performed, in case of suspicion. Plasma HIV-1 RNA viral load, CD4/CD8 count, whole blood cells count, metabolic parameters (fasting triglycerides, total cholesterol, HDL-Cholesterol, and LDL-cholesterol), fasting glycemia, Creatinine, CPK, AST, ALT, bilirubin dosages, urine analysis (proteinuria, albuminuria, creatininuria, glycosuria) will be realized in the local laboratory. Blood samples will be collected for sample bank (plasma, serum and whole blood bank). The patient's quality of life, felt symptoms and adherence will be collected using self-questionnaires.

Patients participating to the DXA-Scan sub-study will perform their third scans. DXA scan might be performed with a time limit up to 10 days before and after the visit date of W96.

- **EOT Visit (End of treatment):** this visit will be realized only in case of giving up or premature stop of trial treatment.

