At this visit, the investigator will realize a clinical examination (blood pressure, heart rate, body temperature, targeted physical examination, weight), anthropometric measurements (abdominal and waist circumference), check the presence of intercurrent pathologies and the treatments intake. Urinary pregnancy test for women of childbearing potential will be performed, in case of suspicion. Plasma HIV-1 RNA viral, CD4/CD8 count, whole blood cells count, metabolic parameters (fasting triglycerides, total cholesterol, HDL-Cholesterol, and LDL-cholesterol), fasting glycemia, Creatinine, CPK, AST, ALT, bilirubin dosages, and urine analysis (proteinuria, albuminuria, creatininuria, glycosuria) will be realized in the local laboratory. Blood samples will be collected for sample bank (plasma, serum and whole blood bank).

The patient's quality of life, felt symptoms and adherence will be collected using self-questionnaires.

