16.2.3 Statistical analysis plan

The number of included patients and the flowchart of the trial will be presented.

The baseline patients' eligibility and characteristics of the ITT population will be described. Quantitative variables will be described by their means, standard deviations, medians, IQR, minimums and maximums. For qualitative variables, figures and percentages per class will be presented or method will be given. All protocol deviations and their reasons will be described.

A detailed statistical analysis plan will be written prior to any analysis of the trial results.

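### LOCF, the only method named for missing continuous data, turns a missing week 48 DXA result into a change of exactly zero and understates the reported size of change

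*Combined protocol and SAP*

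**What the plan says.** Section 16.2.2 compares changes in continuous endpoints in the ITT population with a "two-sided non-parametric paired Wilcoxon test with a 5 % type I error". Missing values are to be handled by "LOCF or other imputation method to be defined in the statistical analysis plan". No other method for missing continuous data is named. Section 16.2.3 adds: "A detailed statistical analysis plan will be written prior to any analysis of the trial results". That separate plan is not part of the documents.

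The measurement schedule decides what LOCF would do:

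- **DXA (section 7.2.1):** "DXA-scans will be performed locally in all participating French sites at D0, W48 and W96". The sub-study has 80 patients. The schedule of assessments marks no scan in the EOT column, and the EOT text in section 11.5.2 lists none.
- **Inflammation markers (section 7.1):** samples are "collected at specific time points: D0, W48, and W96". The schedules in sections 4, 11.1 and 12.1 also mark EOT for these markers and for total HIV-DNA, and the EOT text in section 11.5.2 banks plasma, serum and whole blood.
- **EOT visit (section 11.5.2):** "this visit will be realized only in case of giving up or premature stop of trial treatment".
- **Lipids and fasting glycemia (section 11.1):** also measured at W12 and W24.

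Patients who stop the drug are followed to W96 (section 11.7). Those who give up are not followed further (section 11.9). Those who withdraw consent are excluded from the ITT population (section 16.2.1).

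**The concern.** A carried-forward baseline is not information about week 48. If D0 is a patient's only earlier value, LOCF enters a zero change as if it had been measured. Zeros added in this way pull the summary towards no change and make the data look less variable than they are.

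The endpoints exposed are those behind the trial's second hypothesis (section 5.6): that leaving NRTIs and PIs limits long-term cardiovascular, bone and renal toxicity. A diluted estimate can hide a benefit, and equally a harm such as bone loss.

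**Working it through.** The plan gives no sample size, effect size, SD or missing-data rate for the continuous endpoints, so there is no figure of its own to reproduce.

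**Inputs.** From the documents: n = 80 for DXA, N = 160 for the whole trial, the visit schedule and the paired Wilcoxon test. Assumed: a share f = 5, 10 or 20 % of W48 values missing at random, and a normally distributed change with SD 1 and true mean δ = 0.30 (0.50 as a second case).

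**1. When is the imputed change zero?** Imputed W48 change = last value before W48 minus D0. It is zero whenever D0 is that last value.
- DXA: every missing W48 scan with a D0 scan present. That is 4, 8 or 16 forced zeros among 80.
- HIV-DNA and inflammation markers, N = 160: 8, 16 or 32 zeros if no patient with a missing value has an EOT sample; 4, 8 or 16 if half have one; none if all have one.
- Lipids and glycemia: a W12 or W24 value, where present, is carried instead.
- A missing D0 value cannot be carried and gives no change score.

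**2. Mean.** LOCF mean = (1 − f) × δ. For δ = 0.30 this is 0.95 × 0.30 = 0.285, 0.90 × 0.30 = 0.270 and 0.80 × 0.30 = 0.240. If every patient with a missing value had an EOT sample showing half the W48 change (an assumption), 20 % missing would give 0.80 × 0.30 + 0.20 × 0.15 = 0.270.

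**3. Median.** With a share f of exact zeros, the large-sample median m solves (1 − f) × Φ(m − δ) + f = 0.5 as long as m is positive; otherwise it sits at zero. For δ = 0.30:
- f = 5 %: Φ(m − 0.30) = 0.45/0.95 = 0.474, so m ≈ 0.23.
- f = 10 %: 0.40/0.90 = 0.444, so m ≈ 0.16.
- f = 20 %: 0.30/0.80 = 0.375, so m would be −0.02 and the median is 0.

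Simulated averages at n = 80 are about 0.23, 0.18 and 0.06 (500 trials per setting); 20,000 trials per setting give 0.24, 0.17 and 0.06.

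**4. Standard error and coverage of a mean change.** LOCF variance = (1 − f) + f(1 − f)δ². With n = 80 and δ = 0.30:

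| Missing | LOCF SE | Observed-case SE | Ratio |
|---|---|---|---|
| 5 % | √(0.954/80) = 0.109 | √(1/76) = 0.115 | 0.95 |
| 10 % | √(0.908/80) = 0.107 | √(1/72) = 0.118 | 0.90 |
| 20 % | √(0.814/80) = 0.101 | √(1/64) = 0.125 | 0.81 |

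Simulated coverage of a 95 % interval over δ = 0.30 and 0.50 is about 94–95 %, 92–94 % and 82–91 %. Observed-case coverage stays at 95 %.

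**5. The planned test.** At n = 80 with no EOT value:
- Zeros dropped: the LOCF Wilcoxon p-value equalled the complete-case p-value in every simulated trial.
- Type I error: 4.9–5.1 % with zeros dropped and 4.6–5.4 % with Pratt's handling of zeros.
- Power at 20 % missing and 0.30 SD: 0.624 with Pratt's handling against 0.666 with zeros dropped in one simulation (500 trials), 0.632 against 0.650 in another (3,000 trials).

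**The case against.** Much of the case on the other side stands.

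- **All markers.** A reader might infer that LOCF forces a zero for every missing W48 value of every marker measured at D0, W48 and W96. That is exact only for DXA. A patient who gives up or stops before W48 is due an EOT visit with banked samples, so HIV-DNA and inflammation markers should then have a post-baseline value. Patients who stop the drug also stay on the visit calendar.
- **Withdrawals.** A reader might count consent withdrawals among the affected patients. They are outside the ITT population and are never imputed. The cases left are missed scans or samples, loss to follow-up, and patients in the DXA sub-study who give up.
- **False significance.** A reader might infer from the smaller standard error that the planned test is anti-conservative. Step 5 shows that it is not. Section 16.2.2 plans no confidence interval for continuous changes, so the coverage figures matter only if one is reported.
- **LOCF was used.** The text allows another method and the detailed plan is not available, so use of LOCF cannot be inferred.

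The open choice does not remove the point. One of the options left open gives diluted estimates, and it is the only one named. Appendix A8 already reports first results on lipids, inflammation, weight and bone while section 16.2.2 still carries the either/or wording. These documents therefore do not show which method was fixed, or when.

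**Conclusion.** The point holds for the reported size of change. If LOCF is used, a missing W48 DXA result with a D0 scan counts as no change; the same applies to HIV-DNA and inflammation markers without an EOT sample. The loss in the mean equals the share of forced zeros, and the loss in the median is larger. At 5 % missing the effect is small; at 20 % the median change nearly disappears.

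These sizes rest on assumed missing rates, values missing at random, a normally distributed change and no EOT value. If zeros are dropped, the Wilcoxon p-value is the complete-case one; section 16.2.2 does not say how zeros are treated, and section 16.2.4 leaves three software packages listed. Only secondary endpoints are concerned and the primary conclusion is unaffected. This is a cheap improvement.

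**What to change.** In section 16.2.2, delete LOCF and state:

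1. The paired Wilcoxon test is run on observed pairs.
2. The W48 and W96 changes, with 95 % confidence intervals, are estimated from a repeated-measures mixed model on all observed visits. D0 is one of the responses, visit is a factor and the covariance is unstructured.
3. Skewed markers are analysed on the log scale. HIV-DNA below the detection limit given in section 12.3.3 needs its own rule, because a log transformation does not deal with it.
4. The number of observed and missing values is reported for each endpoint and visit.

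The cost is SAP wording and a little programming; no new data are needed. The downside is that the model assumes data missing at random and a distributional form. The observed-pair Wilcoxon test needs no normality, but it does not protect against values that are missing for reasons linked to outcome. Because Appendix A8 already reports first results, any change of method made after them should be labelled as such.
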